5.5 Efficacy Analysis

This is a phase III study comparing one-year relapse rate after allogeneic HSCT with fludarabine, busulfan and total body irradiation regimen and fludarabine and busulfan regimen in patients with a diagnosis of myeloid malignancies.

5.6 Statistical Hypothesis

The null hypothesis is that the 1 year relapse rate is 34%. It is the goal of this study to show that when fludarabine, busulfan and total body irradiation is used as the regimen the risk of relapse is 40% that of the fludarabine and busulfan regimen. Then, we are seeking a relapse rate of 13.6 % in the in the FluBuTBI regimen arm which is less than that in FluBu regimen arm. Thus, we will evaluate the hypotheses

$$H_0: \theta_A \leq \theta_B$$

$$H_A: \theta_A > \theta_B$$

where θ_A = rate of relapse in Arm A (FluBu) which is assumed to be 0.34,

θ_B = rate of relapse in Arm B (FluBuTBI).

Due to the lack of homogeneity in the outcome as a result of risk status (low versus high), it will be useful to stratified on risk status. Thus, a one-sided log-rank test stratified on risk status will be conducted to ascertain if FluBuTBI reduces the relapse rate from that in over FluBu using a 5% level of significance.

5.7 Primary Endpoint

The primary analysis will include all randomized subjects, classified according to their randomized treatment allocation by the *intent-to-treat* principle. The analysis of relapse or disease progression is planned at one year after accrual is completed. The two regimen arms will be compared utilizing a one-sided log rank test stratified on risk status, and using a level significance level of 0.05.

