3.4 Patient Evaluation

Pre-transplant evaluation must be performed within 30 days of transplantation.

- 3.4.1 History with full details of the patient's prior treatments and responses
- 3.4.2 Physical exam with determination of Karnofsky score and findings related to underlying malignancy
- 3.4.3 Chemistry profile to include serum creatinine, AST, alkaline phosphatase, and bilirubin
- 3.4.4 CBC with differential
- 3.4.5 ABO and Rh
- 3.4.6 Serum pregnancy test, if female gender with child-bearing potential
- 3.4.7 HIV, Hepatitis B, Hepatitis C, CMV serology
- 3.4.8 Disease Staging:
 - 3.4.8.1 Bone marrow aspiration and biopsy
 - 3.4.8.2 Morphology
 - 3.4.8.3 Cytogenetic evaluation
 - 3.4.8.4 Fish study for common abnormalities associated with the disease being treated (if previously documented negative, need not be repeated to comply with this requirement).
 - 3.4.8.5 Molecular testing for common abnormalities associated with the disease being treated
- 3.4.9 Pulmonary function tests with DLCO
- 3.4.10 MUGA scan or cardiac echo
- 3.4.11 EKG

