3.7.5.2 Chimerism studies will be obtained at time of relapse

3.7.5.3 Record of all medication administered during inpatient course

3.8 Post transplant re-staging of disease

3.8.1 Bone marrow aspirate and biopsy with cytogenetic evaluations will be obtained:

3.8.1.1 Day 84 (± 7 days), at one year (± 30 days), and whenever there is evidence of relapse

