3.10.1 Conditioning Regimens

Eligible patients who have signed informed consent will be randomized to treatment arm A (Flu-Bu) or treatment arm B (Flu-Bu-TBI).

3.10.2 Treatment arm A:

- 3.10.2.1 Patients must be admitted to HUMC prior to the start of the fludarabine and will not be discharged until engraftment has occurred.
- 3.10.2.2 Fludarabine will be administered at a dose of 40/mg/m² IV daily for 4 days starting on transplant day -6.
- 3.10.2.3 Busulfan will be administered immediately following the fludarabine at a dose of 130 mg/m² IV daily for 4 days starting on transplant day -6.
- 3.10.2.4 Patients will also receive rabbit antithymocyte globulin (Thymoglobulin) at a dose of 0.5 mg/kg IV on day -3, and 1.5 mg/kg on day -2 and 2 mg/kg on day -1
- 3.10.2.5 Hematopoietic cells will be infused on day 0
- 3.10.2.6 Graft versus host disease (GVHD) prophylaxis will consist of tacrolimus 0.03 mg/kg (or 0.015 mg/kg for age \geq 65) using ideal body weight, IV total daily dose starting on transplant day -2 and adjusted based on blood levels. Methotrexate at a dose of 5 mg/m² IV will be administered on transplant days +1, +3, +6 and +11
- 3.10.2.7 Dose adjustment for the fludarabine, busulfan and antithymocyte globulin will be as follows:
 - 3.10.2.7.1 If patient weighs less than 100% of ideal body weight (IBW), dosing is based on actual body weight
 - 3.10.2.7.2 If patient weighs 120-150% of IBW, dosing is based on adjusted body weight (ABW)
 - 3.10.2.7.3 If patient weighs greater than 150% of IBW, actual weight will be capped at 150% of ideal body weight, and this will be used in the adjusted body weight formula
- 3.10.2.8 Corrected body weight formula: ABW= IBW + [(0.25) x (actual BW-IBW)]

3.10.3 Treatment arm B:

- 3.10.3.1 Patients must be admitted to HUMC prior to the start of the fludarabine and will not be discharged until engraftment has occurred.
- 3.10.3.2 Fludarabine will be administered at a dose of 40/mg/m² IV daily for 4 days starting on transplant day -6.
- 3.10.3.3 Busulfan will be administered immediately following the fludarabine at a dose of 130 mg/m² IV daily for 4 days starting on transplant day -6.
- 3.10.3.4 Total body irradiation will be given in 2 fractions of 200 CGY (total 400 CGY) on day -1.

3.10.3.5 All patients in treatment arm B will also receive rabbit antithymocyte globulin (Thymoglobulin) at a dose of 0.5 mg/kg IV on day -3, and 1.5 mg/kg on day -2 and 2 mg/kg on day -1.

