5 STATISTICAL EVALUATION

5.1 Primary Objective

The primary objective of this single institution randomized Phase III trial is to compare the 1-year relapse rate of myeloid malignancy in patients receiving two different conditioning regimens. In this study, subjects will be randomly assigned to one of 2 conditioning regimens: fludarabine and busulfan or fludarabine, busulfan and low-dose total body irradiation. The myeloid malignancies include acute myeloid leukemia (AML), chronic myeloid leukemia (CML) and other myeloproliferative diseases, and myelodysplastic syndromes (MDS).

Primary endpoint will be the 1-year event free survival (EFS) for the two treatment groups, where the event is relapse or progression. Patients are considered a failure with respect to EFS if they experience disease relapse or progression. The time to this event is the time from transplant to relapse or progression. Subjects alive without confirmed disease progression will be censored at the time of last disease evaluation. Patients who die without evidence of disease relapse or progression will be censored at time of death and death will not be treated as failure for analysis of this primary endpoint.

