5.3 Accrual, Registration and Follow-up

The targeted sample size is 54 subjects. It is estimated that four years of accrual will be necessary to enroll this number of subjects. About 50 patients (49-52) underwent allogeneic transplantation at this center, indicating that an appropriate number of subjects will be available to complete this study in the time frame anticipated. Subjects will enroll uniformly over the accrual period. The randomization will be stratified by relapse risk status (high versus low). Low relapse will include: AML CR1 and CML chronic phase. All other AML, MPD and MDS patients will be considered high relapse risk. An AML CR1 patient with a history of MDS will be considered high relapse risk. All patients who are Flt3/ITD positive at any time will be considered high relapse risk. Upon establishing eligibility, subjects will be randomized in equal numbers to the FluBu and FluBuTBI arms using permuted blocks within strata.

All subjects will be followed for one year from time of transplantation, during which they will be monitored for the effects of treatment through regular clinic visits. Additional follow-up data beyond one year of progression-free survival will be obtained from HUMC Cancer Center Database.

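### The primary analysis is timed from the end of accrual, but relapse is timed from transplant and the 1-year marrow may run to day 395, so one or two late patients may be analysed too early and days 366-395 have no counting rule

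*Combined protocol and SAP*

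**What the plan says.** Section 5.7 fixes the timing of the primary analysis: "The analysis of relapse or disease progression is planned at one year after accrual is completed". Other sections set the clocks that this has to fit.

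- **Time origin (5.1):** "The time to this event is the time from transplant to relapse or progression".
- **Censoring (5.1):** "Subjects alive without confirmed disease progression will be censored at the time of last disease evaluation". The plan does not define what counts as a disease evaluation.
- **Scheduled marrows (3.8):** "Day 84 (± 7 days), at one year (± 30 days), and whenever there is evidence of relapse". The 1-year marrow may therefore fall on any day from 335 to 395.
- **Follow-up (5.3):** "All subjects will be followed for one year from time of transplantation", and then "Additional follow-up data beyond one year of progression-free survival will be obtained from HUMC Cancer Center Database".
- **Randomization to transplant:** patients are randomized once eligible (5.3). Fludarabine and busulfan are then given "IV daily for 4 days starting on transplant day -6" (3.10), so transplant comes at least 6 days after randomization. No upper limit is stated. The nearest figure is in 3.4: "Pre-transplant evaluation must be performed within 30 days of transplantation".

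The primary test is a one-sided log-rank test stratified on risk status (5.6, 5.7). Sections 5.1 and 5.4 describe the endpoint in 1-year terms, and 5.2 has the probability of relapse estimated by cumulative incidence. No section says how a relapse first seen on days 366-395 counts towards the 1-year figure.

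**The concern.** The analysis clock starts at the last enrolment, while the endpoint clock starts at the last transplant and its final scheduled test may come 395 days later. A patient enrolled near the end can thus be fully compliant and still lack the 1-year marrow at the data cut. That patient is censored at the last disease evaluation. If only marrows count as evaluations, this could be as early as day 84.

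There is also a classification gap. The same disease found at the scheduled marrow on day 360 is a relapse within 1 year, but on day 370 it falls outside an estimate read at day 365. The appointment date would then affect the reported 1-year relapse rate, which is the quantity named in the primary objective (2.1).

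**Working it through.** **The plan's own figure.** Section 5.4 gives 80.06% power with 26 per arm: one-sided 5%, 1-year relapse of 34% versus 13.6%, 4 years of accrual, 1 year of follow-up, 10% dropout. I took exponential hazards and read the dropout as 10% per year.

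- Hazards: hA = -ln(0.66) = 0.4155 and hB = -ln(0.864) = 0.1462, so HR = 0.352. Dropout: d = -ln(0.9) = 0.105.
- Chance of an observed relapse, for uniform accrual over 4 years and shortest follow-up F: p(h) = h/(h+d) × [1 - e^(-(h+d)F) × (1 - e^(-4(h+d))) / (4(h+d))].
- With F = 1 year, so that each patient contributes 1-5 years: pA = 0.599 and pB = 0.296. Expected relapses = 26 × 0.895 = 23.3.
- Schoenfeld power = Φ(|ln HR| × √(D/4) - 1.645) = 80.9%, close to the stated 80.06%.
- With every patient capped at 1 year, power is 55.9% at 26 per arm. At 27 per arm it is 57.2%, with 12.2 relapses.

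Other formulas with 1-5 years of follow-up give 74.8% (Freedman) and 76.1% (Lachin-Foulkes). Freedman without dropout gives 79.7%. Every calculation that comes near 80% counts relapses beyond year 1.

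**Patients analysed too early.** Accrual is 54/4 = 13.5 per year, or 0.0370 per day, uniform as stated in 5.3. Let L be the days from randomization to transplant. L is at least 6; the upper value of 30 is an assumption borrowed from the work-up window. A patient randomized u days before accrual ends is at day 365 + u - L when the data are cut.

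| Quantity | Formula | L = 6 | L = 30 |
|---|---|---|---|
| Not yet at day 365 | 0.0370 × L | 0.2 | 1.1 |
| Marrow window still open | 0.0370 × (30 + L) | 1.3 | 2.2 |
| Expected to lack the marrow, dates uniform on days 335-395 | 0.0370 × (30 + L)²/120 | 0.4 | 1.1 |

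The last row comes from integrating (30 + L - u)/60, the chance that the marrow is still to come, over u from 0 to 30 + L.

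**Effect of moving the cut (27 per arm, same formula).**

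| Data cut | Shortest follow-up | Relapses | Power |
|---|---|---|---|
| As written, L = 30 | 335 days | 23.8 | 81.6% |
| As written, L = 6 | 359 days | 24.1 | 82.1% |
| Last transplant + 395 days | 395 days | 24.5 | 82.7% |

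**Late-window relapses.** Under the design hazards, ignoring dropout and death, relapses arising on days 84-365 are 27 × (e^(-0.4155 × 84/365) - 0.66) = 6.7 in the FluBu arm and, in the same way, 2.8 in the FluBuTBI arm: 9.5 in all. The documents do not say what share would first be seen at the 1-year marrow. If it is 10-50% (an assumption) and half of those marrows fall after day 365, then 9.5 × 0.10 × 0.5 = 0.5 to 9.5 × 0.50 × 0.5 = 2.4 relapses would be dated after day 365. First-year relapses total about 27 × (0.34 + 0.136) = 12.9.

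**The case against.** The strongest reply is that little is lost, and most of it stands.

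- A reader might infer that follow-up stops at 1 year. It does not: 5.3 goes on to provide database follow-up beyond that point. What remains is that this source has no assessment schedule and no section links it to the primary analysis.
- A reader might infer that a relapse on days 366-395 is lost from the primary test. The documents do not support this. No section truncates the log-rank test at day 365, and the power figure points to longer observation. Only a 1-year estimate read at day 365 would miss such a relapse.
- A reader might infer that the last patients are dropped, or all analysed without the marrow. They are censored, not excluded, and even the very last patient is at day 335-359 at the cut (L from 30 to 6), so the window has already opened.
- The scheduled marrow is not the only route to detection. Section 3.8 also requires one at any evidence of relapse, and 3.7 has visits and chimerism at 6, 9 and 12 months.
- The schedule is the same in both arms, so there is no argument here for differential bias.

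The mismatch between the analysis clock and the endpoint clock survives all of this, as does the missing rule for days 366-395.

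**Conclusion.** The concern holds as a small timing defect that is cheap to repair. The cut in 5.7 comes 36-60 days before the last patient's marrow window closes. It leaves 0.2-1.1 patients short of day 365, 1.3-2.2 with the window open, and about 0.4-1.1 without the marrow. Moving it gains 0.5-0.8 of a relapse and about 1 point of power. The missing rule for days 366-395 affects the reported 1-year proportion by perhaps 0.5-2.4 relapses, a range that depends on an assumed share.

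These sizes rest on uniform accrual (stated), a lag of 6-30 days (upper value assumed), uniform marrow dates (assumed) and exponential hazards at the design rates. It would go too far to say that the trial has only 57% power. That would follow only if the log-rank analysis were capped at 1 year, which the plan does not state. The figure does show why a repair must not introduce such a cap.

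**What to change.** 1. In 5.7, set the data cut-off for the primary analysis at the last patient's transplant plus 395 days.
2. In 3.1 and 5.3, extend protocol follow-up to completion of the 1-year marrow.
3. For the 1-year relapse proportion only, state that the result of the scheduled day 335-395 marrow gives 1-year status. This credits a patient with a clear marrow on day 335 with up to 30 unobserved days, an acceptable convention if stated in advance.
4. In 5.1 and 5.7, state that the stratified log-rank test uses actual relapse and censoring times, with no truncation or backdating at day 365, and that the post-year-1 database data enter it.

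The cost is protocol and SAP wording and a final analysis 36-60 days later (30 days plus the lag), about 1-2 months. No extra tests are needed.

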5.8 Secondary Endpoints

5.8.1 Secondary endpoints will include:

5.8.1.1 Overall response rates: Defined as the composite endpoint of response to treatment which includes Complete Response (CR), Partial Response (PR), stable disease (SD) as defined in International Response Criteria. We will also analyze Complete Response rate.

5.8.1.2 Overall survival (OS): Defined as time from the first dose of administration to death from any cause.

5.8.1.3 Univariate analysis of the risk of progression/relapse and mortality: In addition, multivariate analysis of the risk of progression/relapse and overall mortality will be conducted to assess influence of variables measured after the start of treatment.

5.8.1.4 Regimen-related toxicity: Graded and presented in a descriptive nature.

5.8.2 Overall Survival

The event is death from any cause. The time to this event is the time from randomization to death, loss to follow-up or the end of the study, whichever comes first. Patients alive at the time of last observation are considered censored. The Kaplan-Meier estimate of survival will be estimated separately for each treatment-

group and risk status. A log-rank test stratified on risk status, conducted at a one-sided significance level of 0.05 analogous to the analysis of relapse risk described above.

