5.4 Sample Size and Power Calculations

The main objective is to compare the relapse-free surviving proportions at 1 year in myeloid malignancy patients who are randomized to either FluBuTBI or FluBu conditioning regimen.

In examining the time to relapse, we consider an analysis of the proportion surviving without relapse/progression at the 1 year endpoint. A comparison of this event between the two treatment arms will be conducted using log-rank test statistics at the 5% level of significance. Based on this statistic, the calculation of sample size was obtained using PASS 2008. According to the results from previous studies [De Lima et al], the 1-year relapse rate in patients with myeloid malignancies being treated with FluBu is 34%. We posit that when the FluBuTBI regimen is used the relapse rate will be reduced to 13.6%, which is 40% of the relapse risk in the FluBu regimen arm. Then, a one-sided log-rank test will be used to examine evidence for a reduction in disease relapse. For the nominal power of 80%, significance level of 5%, 4 year accrual, 1 year follow-up and 10% drop out rate in both FluBuTBI and FluBu treatment arm, 52 patients (26 per arm) will be required to detect the 20.4 difference (60% reduction in relapse rate). This calculation achieved 80.06%. To adjust for balanced samples within the risk status, the study will enroll a maximum of 54 patients (27 per arm).

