5.8.4 Event-Free Survival

The event is death from any cause or relapse/disease progression. The time to this event is the time from randomization to death, relapse or disease progression, loss to follow-up or the end of the study, whichever comes first. Patients alive at the time of last observation are considered censored. The Kaplan-Meier estimate of survival will be estimated separately for each treatment-group and risk status. A one-sided log-rank test stratified on risk status will be conducted at the 5% level of significance, analogous to the analysis of relapse risk described above.

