5.10 Stopping Rules

If the non-relapse mortality rate in the experimental group receiving TBI within the first 3 month post exceeds 20% then the study will be stopped. It is assumed that the NRM in the standard FluBu conditioning regimen is 10%. Resumption of patient accrual will only be permitted after review of interim results by the Institutional Review Board and the Data Safety Monitoring Board

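### The designated overall survival and event-free survival tests are one-sided for benefit, so they have no rejection region for harm, and no confidence interval for the randomized survival contrast is planned

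*Combined protocol and SAP*

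**What the plan says.** OS is tested in section 5.8.2: "A log-rank test stratified on risk status, conducted at a one-sided significance level of 0.05 analogous to the analysis of relapse risk described above". EFS is tested in section 5.8.4, where the event is death or relapse/progression: "A one-sided log-rank test stratified on risk status will be conducted at the 5% level of significance". Neither section states a direction; both refer back to the relapse analysis.

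That analysis does have a direction. Section 5.4 says "a one-sided log-rank test will be used to examine evidence for a reduction in disease relapse", section 5.6 takes a higher relapse rate in the FluBu arm as the alternative, and section 5.7 has the arms "compared utilizing a one-sided log rank test stratified on risk status, and using a level significance level of 0.05".

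Two further places bear on the point. Section 5.1 defines the primary endpoint so that a patient who dies without relapse is censored at death and is not a failure. (It also calls that endpoint event-free survival; here EFS means the 5.8.4 endpoint.) Section 5.10 halts the study if 3-month non-relapse mortality (NRM) in the TBI arm exceeds 20%, and adds: "It is assumed that the NRM in the standard FluBu conditioning regimen is 10"%.

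**The concern.** A one-sided test is arguable for relapse, where added conditioning is expected to act in one direction. Survival is the net of two effects that may oppose each other: fewer relapse deaths and more non-relapse deaths. The background sections describe this trade-off between regimens. In 1.1, reduced-intensity conditioning had more relapse and less non-relapse mortality. In 1.2, FluBu had treatment-related mortality of 12% against 34% with BuCy, but relapse of 42% against 20%.

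Because the primary test censors deaths without relapse, OS and EFS are the designated log-rank comparisons in which such deaths count against TBI. With all 5% on the benefit side, any excess of deaths on TBI, however large, comes out of these two tests as a non-rejection. A significant relapse reduction could then stand beside non-significant OS and EFS results when survival on TBI is in fact worse.

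**Working it through.** **1. The plan's own figure.** No power is stated for OS or EFS. The stated power is 80.06% for relapse with 26 per arm. Inputs from 5.4: 1-year relapse 34% and 13.6%, one-sided 5%, 4-year accrual, 1-year follow-up and 10% dropout, read here as 10% per year.
- Hazards: −ln(0.66) = 0.4155 and −ln(0.864) = 0.1462; hazard ratio (HR) 0.1462/0.4155 = 0.352.
- Event probabilities with uniform accrual: 0.599 and 0.296; expected events 26 × (0.599 + 0.296) = 23.3.
- Schoenfeld power: Φ(√(23.3/4) × |ln 0.352| − 1.645) = Φ(2.52 − 1.645) = 80.9%, close to 80.06%.
- With a two-sided 5% test (1.96) it is 71.2%.

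The sample size therefore rests on the one-sided relapse test. Changing OS and EFS does not affect it.

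**2. Direction of the OS and EFS tests.** Read together, 5.4, 5.6, 5.8.2 and 5.8.4 give rejection only when Z < −1.645, with negative Z meaning fewer events on FluBuTBI. The probability of declaring harm is zero by construction.

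**3. Effect of a 5% harm tail on OS.** From the plan: 27 per arm and a test stratified on risk status. Assumed, because the documents do not give them: control 1-year mortality 30%, exponential survival, 70% high-risk patients, censoring at 1 year.

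Closed-form check: HR = ln(1 − p_TBI)/ln(0.70); deaths D = 27 × (0.30 + p_TBI); harm power = Φ(√(D/4) × ln HR − 1.645).
- 40%: HR 1.43, D 18.9, Φ(0.78 − 1.645) = 19%
- 50%: HR 1.94, D 21.6, Φ(1.54 − 1.645) = 46%
- 60%: HR 2.57, D 24.3, Φ(2.33 − 1.645) = 75%

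For benefit at 15%: HR 0.456, D 12.15, Φ(1.37 − 1.645) = 39%.

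Simulated stratified log-rank tests agree:

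| 1-year mortality, FluBu v FluBuTBI | Declares harm, as planned | Declares harm, with 5% harm tail | Declares benefit, either version |
|---|---|---|---|
| 30% v 15% | 0 | 0.1% | about 37% |
| 30% v 40% | 0 | about 19% | under 1% |
| 30% v 50% | 0 | about 43% (43–45% over runs) | 0.1–0.2% |
| 30% v 60% | 0 | about 74% (73–74%) | 0.0% |

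The benefit boundary stays at −1.645, so the last column is the same under both versions.

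**4. Sensitivity.** Other control rates give similar results for a 20-point excess: 49% for 20% v 40% and 44% for 40% v 60%. Section 5.8.2 follows OS to the end of the study. With follow-up of 1 to 5 years and no dropout, detection of 50% and 60% mortality rises to 66% and 90%.

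**5. What an interval would show.** The approximate 90% limits are HR × exp(±1.645 × 2/√D). With 20 deaths (assumed) the factor is exp(0.736) = 2.09. An observed HR of 2.0 would carry an interval of about 2.0/2.09 to 2.0 × 2.09, or 0.96 to 4.2. That is not significant, but it says far more than a benefit-only p-value.

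**The case against.** The strongest reply is that mortality by arm is examined elsewhere. Section 5.8.5 plans a Cox analysis of treatment-related and overall mortality, with regimen among the covariates, a 0.05 criterion with no stated direction, and relative risks. Sections 5.8.2 and 5.8.4 plan Kaplan-Meier estimates by arm, 5.2 plans cumulative incidence of treatment-related mortality, and 5.8.6.1 compares incidence, including treatment-related mortality, between arms and reports to the DSMB. A reader might infer from the one-sided tests that the trial has no means of finding that TBI shortens survival. These provisions rule that reading out.

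They do not close the gap. In 5.8.5 regimen is only a candidate under backward selection and may be dropped. GVHD arises after transplant and enters as a time-dependent covariate, so a retained regimen effect is not a clean randomized contrast. The relative risks come with p-values, and no interval is mentioned. Section 5.8.6.1 names no test, and the 95% intervals in 5.8.6 are for toxicity incidence.

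A reader might also take 5.10 as evidence that TBI raises early mortality. It is a safety limit and shows nothing about the actual rate. The one series described with fludarabine, busulfan and 400 cGy TBI had 3% treatment-related mortality (1.2). That series was 64 adults with acute leukemia in first or second remission, whereas this trial admits any disease stage (3.2.1.2), so it does not settle the direction either.

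Finally, sidedness is not the main limit on detecting harm. The only mortality contrast in the documents is 10 points (10% v 20% NRM). A 10-point excess over 30% would be found in only about 19% of trials even with the harm tail. That objection stands, and it moves the weight of the fix to the interval.

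**Conclusion.** The point holds for the two designated tests: by analogy with the relapse hypothesis, the OS and EFS log-rank tests cannot reject for harm, and the plan provides no confidence interval for the randomized survival contrast. It does not extend to a claim that the trial could never detect worse survival. Adding the tail raises the chance of declaring harm from zero to about 19%, 43% and 74% at 40%, 50% and 60% TBI mortality. These figures rest on the assumed 30% control mortality, 70% high-risk share, exponential survival and 1-year censoring. The absence of a harm region depends on none of them; it depends only on reading the unstated direction in 5.8.2 and 5.8.4 as that of the relapse test. The change is cheap and worth making, but it would not make a trial of 54 patients sensitive to modest harm.

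**What to change.** Leave the primary relapse test in 5.7 as it is. In 5.8.2 and 5.8.4:

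- State the direction, and make the stratified log-rank test two-sided with 5% in each tail, so that the benefit criterion is kept and harm can be declared.
- Report the stratified hazard ratio with a two-sided 90% confidence interval, which matches that test. A 95% interval can be shown as well.
- Base the hazard ratio on the randomized arms and risk stratum only, separate from the model selection in 5.8.5.

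The cost is a few sentences of text. It needs no additional patients, loses no power for benefit and leaves the sample size unchanged. The downside is a total two-sided error of 10% on these secondary tests, which should be stated openly. If that is unwelcome, the hazard ratio with its interval alone would still supply the more important part.
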